### **6.1.5. Timing of Primary Analysis**

#### **6.1.5.1. Part 1 Primary Analysis**

To ensure that all primary and key secondary endpoints are well-powered, database lock for the primary and key secondary endpoints in Part 1 (the Part 1 Primary Database Lock) will be triggered when at least 300 facility residents have been enrolled and when 33 participants in the Part 1 Prevention population experience a moderate or worse severity case of COVID-19. All pre-specified analyses will be based on the Primary Database Lock. However, if the accumulation of moderate or worse severity cases of COVID-19 occurs slower than expected, the Primary Database Lock may be triggered when at least 36 participants in the Part 1 Prevention population test positive for SARS-CoV-2 within 4 weeks of randomization. If this is the case, only the primary endpoint will be evaluated at the Primary Database Lock. At the time of the primary analysis for Part 1, only data from patients enrolled in Part 1 will be unblinded to the sponsor.

To account for participants who have not finished the Evaluation Period at the time of the Primary Database Lock, a supplementary database lock (the Part 1 End of Evaluation Database Lock) will occur once all participants have completed the Evaluation Period or discontinued from the study. The analyses conducted during the Primary Database Lock will be re-evaluated at the End of Evaluation Database Lock.

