9.2. Sample Size Determination

For Part 1, an estimated 33 events are needed to show superiority of LY3819253 4200 mg over placebo in each of the primary and key secondary endpoints, using the formula by Schoenfeld (1983). An average sample size of approximately 1300 participants who are SARS-CoV-2 PCR negative and serology negative at baseline is expected to obtain the needed number of events for each endpoint.

For Part 2, an estimated 56 events in the Prevention Cohort are needed to show superiority over placebo for either LY3819253 700 mg or LY3819253 350 mg+LY3832479 700 mg in each of the primary and key secondary endpoints. Approximately 2000 participants on average will be randomly assigned to study intervention such that approximately 1700 participants are randomized in the Prevention Cohort with the goal of achieving approximately 56 events on each of the primary and key secondary endpoints.

Due to the dynamic nature of the pandemic, Part 3 will enroll at least 30 participants and up to approximately 500 participants randomized to either LY3819253 700 mg or LY3819253 700 mg + LY3832479 1400 mg. Part 3 of the study is considered exploratory and is not powered for inference between the two treatment arms.

The maximum sample size for this study is approximately 5000 participants in the intent-to-treat (ITT) population.

Participants will be residents and staff of skilled nursing and assisted living facilities. Globally, there are many reports of the rapid spread of COVID-19 amongst residents of skilled nursing facilities following identification of an index case, with high associated rates of morbidity and mortality (Arons et al. 2020; Grabowski). Given that residents at these facilities are at higher risk for having a more severe disease course of COVID-19, this will be an important population to participate in the study. Therefore, a minimum of 300 residents will be enrolled.

Operationally, this will be accomplished, when possible, by identifying facilities where approximately half of the participants interested in the study are residents.

For sample size determination for Part 1, the following assumptions were used:

- 1) two-sided significance level of 0.05;
- 2) 90% power for the primary and key secondary endpoints;
- 3) an 8-week placebo group event rate of 4.0% for moderate or worse severity COVID-19;

4) a risk ratio of 0.33 between LY3819253 and placebo in terms of the primary and key secondary endpoints.

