## **5.2. Determination of Sample Size**

For Part 1, an estimated 33 events are needed to show superiority of LY3819253-4200mg over placebo in each of the primary and key secondary endpoints, using the formula by Schoenfeld (1983). An average sample size of approximately 1300 participants who are SARS-CoV-2 PCR negative and serology negative at baseline is expected to obtain the needed number of events for each endpoint.

For Part 2, an estimated 56 events in the Prevention Cohort are needed to show superiority over placebo for either LY3819253-700mg or LY3819253-350mg+LY3832479-700mg in each of the primary and key secondary endpoints. Approximately 2000 participants on average will be randomly assigned to study intervention such that approximately 1700 participants are randomized in the Prevention Cohort with the goal of achieving approximately 56 events on each of the primary and key secondary endpoints.

The maximum sample size for this study is approximately 5000 participants in the intent-to-treat (ITT) population.

Participants will be residents and staff of skilled nursing and assisted living facilities. Globally, there are many reports of the rapid spread of COVID-19 amongst residents of skilled nursing facilities following identification of an index case, with high associated rates of morbidity and mortality (Arons et al. 2020; Grabowski). Given that residents at these facilities are at higher risk for having a more severe disease course of COVID-19, this will be an important population to participate in the study. Therefore, a minimum of 300 residents will be enrolled.

Operationally, this will be accomplished, when possible, by identifying facilities where approximately half of the participants interested in the study are residents.

For sample size determination for Part 1, the following assumptions were used:

- 1) two-sided significance level of 0.05;
- 2) 90% power for the primary and key secondary endpoints;
- 3) an 8-week placebo group event rate of 4.0% for moderate or worse severity COVID-19;
- 4) a risk ratio of 0.33 between LY3819253 and placebo in terms of the primary and key secondary endpoints.

For sample size determination for Part 2, the following assumptions were used:

- 1) two-sided significance level of 0.025;
- 2) 90% power for the primary and key secondary endpoints;
- 3) an 8-week placebo group event rate of 5.3% for moderate or worse severity COVID-19;

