### ***6.3.2. Missing COVID-19 Status or Disease Severity***

For the primary and key secondary endpoints, if a participant has at least one post-baseline RT-PCR test result and has not yet met the criterial for COVID-19 or is missing data used to determine COVID-19 status, the participant will be treated as not experiencing COVID-19. The same logic will be used for moderate-or-worse severity COVID-19.

As a supplementary analysis on these endpoints, the approach described in Section [6.3.1](#) will be used to handle missing COVID-19 status or disease severity due to death unrelated to COVID-19, study discontinuation, or the triggering of the Primary Database Lock. Participants with missing information will be treated as not experiencing the associated endpoint event and will be weighted based on the proportion of the Evaluation Period that was completed.

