## 6.10. Efficacy Analyses

### 6.10.1. Primary Outcome and Methodology

The endpoint for the primary analysis is defined as the first occurrence of COVID-19, defined as the detection of SARS-CoV-2 by reverse transcription – polymerase chain reaction (RT-PCR) AND mild or worse disease severity within 21 days of detection, by Day 57 (8 weeks after randomization).

The percentage of patients in the Prevention population who experience COVID-19 by Day 57 will be summarized by treatment group.

Statistical comparison between each study intervention and placebo will be done using a logistic regression model. The model will include treatment, facility, role within the facility (resident vs staff) and sex as fixed effects. The odds ratio and the corresponding CIs, as well as the treatment differences and the corresponding CIs, will be computed using the Wald method and reported. A p-value from the Rao's score test will be reported.

As an exploratory analysis, the incidence of COVID-19 within 21 days of randomization will be compared across treatment groups in the subset of participants in the Treatment population who are asymptomatic at baseline (as defined in Table 1 of the protocol). Statistical comparisons will use similar methodology as described in Section 6.10.1.

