#### **6.10.3.2. Incidence of SARS-CoV-2 Infection by Day 29**

As a key secondary endpoint, the proportion of patients in the Prevention populations who are SARS-CoV-2 positive postbaseline (Table PYAD.4.1) by Day 29 will be summarized by treatment group. Similar methodology, as described in Section 6.10.1 will be utilized for statistical hypothesis testing, following the testing scheme described in Section 6.5.

Results of SARS-CoV-2 tests during the study will be listed for each participant.

As a sensitivity analysis, the percentage of patients in the Prevention population who experience death or are SARS-CoV-2 positive postbaseline by Day 29 will be summarized by treatment group. Similar methodology, as described in Section 6.10.1 will be utilized for statistical hypothesis testing.

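### The Part 1 fallback lock counts 4-week infections, tests COVID-19, and sets no minimum number of primary events

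*SAP*

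**What the plan says.** **Planning basis.** SAP 5.2 states that "an estimated 33 events are needed to show superiority of LY3819253-4200mg over placebo in each of the primary and key secondary endpoints". It uses Schoenfeld's formula with a "two-sided significance level of 0.05" and a risk ratio of 0.33. Protocol 9.2 gives the same basis, with "90% power for the primary and key secondary endpoints".

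**Main trigger.** SAP 6.1.5.1 opens with the aim that every primary and key secondary endpoint should be well powered. The lock comes when 33 Part 1 Prevention participants have moderate-or-worse COVID-19 and at least 300 residents are enrolled.

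**Fallback trigger.** If moderate-or-worse cases accumulate too slowly, the lock "may be triggered when at least 36 participants in the Part 1 Prevention population test positive for SARS-CoV-2 within 4 weeks of randomization". In that case "only the primary endpoint will be evaluated at the Primary Database Lock".

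**The two endpoints.** SAP 6.10.3.2 covers infection by Day 29: "As a key secondary endpoint, the proportion of patients in the Prevention populations who are SARS-CoV-2 positive postbaseline". The primary endpoint in SAP 6.10.1 is RT-PCR detection "AND mild or worse disease severity within 21 days of detection, by Day 57".

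**Participants without the event at the lock.** Under SAP 6.3.2, someone with at least one post-baseline RT-PCR result who has not yet met the COVID-19 criteria is still analysed: "the participant will be treated as not experiencing COVID-19".

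**Later look.** SAP 6.1.5.1 adds a supplementary End of Evaluation Database Lock, at which the analyses are repeated.

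**The concern.** The main trigger protects the primary endpoint. Every moderate-or-worse case is also a mild-or-worse case, so 33 of the former imply at least 33 primary events.

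The fallback has no such property. It counts infections, then tests a disease endpoint. A positive who stays asymptomatic adds to the 36 without adding a primary event, and Protocol 4.1 itself notes that infected facility staff may be asymptomatic. A positive whose symptoms have not yet appeared at the lock is also a non-event in that analysis. For participants who need a legally authorised representative, Protocol 8.1.2 records only five observable symptoms, which may lower the share classed as mild.

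At stake is the power of the Part 1 primary test. All pre-specified analyses rest on the Primary Database Lock, and under SAP 6.5 the key secondary endpoints can be tested only if the primary endpoint succeeds.

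**Working it through.** **Inputs from the documents:** two-sided alpha 0.05, power 90%, risk ratio 0.33, 33 events (SAP 5.2, Protocol 9.2); 1:1 allocation (Protocol 6.3); 36 positives within 4 weeks (SAP 6.1.5.1).

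**Inputs not in the documents, so assumed over a range:**
- s, the share of positives who meet the mild-or-worse criteria by the lock;
- L, the number of week 5-8 infections observed by the lock, given the same share s.

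The only placebo rate stated for Part 1 is 4.0% for moderate-or-worse COVID-19. None is given for mild-or-worse disease or for 4-week infection, so neither s nor L can be derived from the plan.

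**Step 1. Reproduce the planned figure.** With 1:1 allocation, Schoenfeld's formula gives

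d = 4 × (1.960 + 1.282)² / (ln 0.33)² = 34.2 events.

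The corresponding power is

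Power = Φ( √(d/4) × |ln 0.33| − 1.96 ).

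At d = 33 this is 89.0%. The plan's 33 events and 90% are therefore consistent to rounding, and 33 events is a fair benchmark.

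**Step 2. Primary events at the fallback lock.**

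Events = s × (36 + L).

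**Step 3. Events and power at risk ratio 0.33, two-sided 0.05.**

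| s | L = 0 | L = 5 | L = 10 | L needed for 33 events (33/s − 36) |
|---|---|---|---|---|
| 50% | 18.0 events, 65% | 20.5, 71% | 23.0, 76% | 30 |
| 60% | 21.6, 73% | 24.6, 79% | 27.6, 83% | 19 |
| 70% | 25.2, 79% | 28.7, 84% | 32.2, 88% | about 11 |
| 80% | 28.8, 84% | 32.8, 89% | 36.8, 92% | about 5 |

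**Step 4. What the 36 infections alone would need.** With L = 0, reaching 33 events requires s ≥ 33/36 = 92%.

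**Step 5. Effect of an event floor.** If the fallback also required 33 mild-or-worse events, power at the lock would be at least 89.0% whatever s and L turn out to be.

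**The case against.** The strongest reply is that the fallback is an openly stated contingency. It is permissive, applies only under slow accrual, says at least 36 so the sponsor may wait for more, and makes no claim to keep 90% power. The plan calls 33 an estimate, and the Protocol synopsis calls it a goal of approximately 33. The synopsis also keeps Part 1 enrolling until the needed events and the resident minimum are reached. Cases in weeks 5-8 can close the gap, and the End of Evaluation lock will pick up late and pending ones. The lowest powers in the table assume no late infections, and no document supports a share as low as 50%.

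Much of this stands. A shortfall is possible, not certain, and the table is illustrative. Treating pending cases as non-events is also not peculiar to the fallback; it applies at any Primary Database Lock.

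It does not remove the mismatch. The synopsis rule governs enrolment, not this lock. Late infections may help, but the trigger does not require any. The End of Evaluation lock is labelled supplementary, and Part 1 data are already unblinded to the sponsor at the primary analysis. A pre-specified route to the primary test should serve the aim with which its own section opens.

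**Conclusion.** The concern holds. The fallback counts a key secondary endpoint, tests only the primary endpoint, and sets no floor on primary events. It therefore does not secure the 33 events behind the stated power.

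Over the assumed ranges (s from 50% to 80%, L from 0 to 10), power at the Primary Database Lock lies between 65% and 92%, against 89% at 33 events. That spans a clear shortfall and none at all, and the rule does not control which occurs. The figures rest on the plan's risk ratio of 0.33 and on late infections having the same symptomatic share as early ones.

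The effect is on power, not type I error, and is confined to the optional route. This should be fixed, and the fix is cheap.

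Two smaller points need clarification only. The fallback sentence does not repeat the 300-resident condition, although SAP 5.2 and Protocol 9.2 set that minimum for enrolment. It also does not say at which lock the key secondary endpoints are tested if the fallback is used.

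**What to change.** In SAP 6.1.5.1, allow the fallback lock only when at least 33 Part 1 Prevention participants have met the mild-or-worse COVID-19 primary endpoint, either in place of the 36 infections or as a second condition beside them. In the same paragraph, state that the 300-resident minimum applies to the fallback too, and name the lock at which the key secondary endpoints are tested under SAP 6.5 when the fallback is used.

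The cost is about two sentences of SAP text. The downside is a possibly later lock under slow accrual, the situation for which the fallback was written.

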#### **6.1.5.2. Part 2 Primary Analysis**

Database lock for the primary and key secondary endpoints in Part 2 (the Part 2 Primary Database Lock) will be triggered when 56 participants in the Part 2 Prevention population experience a moderate or worse severity case of COVID-19. All pre-specified analyses for participants in Part 2 will be based on the Part 2 Primary Database Lock.

To account for participants who have not finished the Evaluation Period at the time of the Primary Database Lock, a supplementary database lock (the Part 2 End of Evaluation Database Lock) will occur once all participants have completed the Evaluation Period or discontinued from the study. The analyses conducted during the Primary Database Lock will be re-evaluated at the End of Evaluation Database Lock.

## **6.2. Adjustments for Covariates**

Unless otherwise specified, efficacy analyses will adjust for the baseline value of the endpoint when modeling estimates and calculating p-values.

## **6.3. Handling of Dropouts or Missing Data**

The SoA, outlined in the protocol, specifies the allowable windows for assessments. Assessments performed outside these windows will not be excluded from any analysis but may be reported as a protocol deviation (see Section [6.14](#)).

### ***6.3.1. Missing SARS-CoV-2 Infection Status***

For the primary and key secondary endpoints, participants in the Prevention population with zero post-baseline RT-PCR test results will be excluded. If a participant has at least one post-baseline RT-PCR test result and has not yet tested positive or is missing additional test results during the time frame of the endpoint, the participant will be treated as SARS-CoV-2 negative at all visits before the last available RT-PCR test, and will be treated as not experiencing the event of interest in the primary and key secondary analyses.

As a supplementary analysis on the key secondary endpoint for incidence of SARS-CoV-2 infection, weights equal to the proportion of the Evaluation Period completed will be used in the logistic regression analysis. If a participant has a missing SARS-CoV-2 Infection Status due to death, study discontinuation, or the triggering of the Primary Database Lock, the participant will be treated as SARS-CoV-2 negative with a weight equal to the proportion of the Evaluation Period (up to Day 29) completed prior to the discontinuation event or the Database Lock.

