Vital signs	X	Daily										X	X	X		Documentation of hospital-based exam is acceptable. Includes: body temperature, pulse rate, BP, SpO ₂ , respiratory rate, FiO ₂ if known, and method of delivery, if applicable. Record while participant is at rest.

Procedures	Screening	Evaluation Period										ETV	Post-Evaluation Follow-Up			Comments
Study Day	Max 7-day window	1	2-7	8	15	22	29	36	43	50	57		85	141	169	
Visit window (\pm number of days)	--	--	--	2	2	2	2	2	2	2	2		7	7	7	
Hospitalization events		Daily										X	X	X		Record if the following events occur: 
Emergency room visitshospitalizedICU admittance,Extended care facility admittance,and discharge for any of the above
Clinical status and concomitant procedures of special interest in hospitalized participants		Daily										X	X	X		Documentation from hospital records is acceptable. Includes: consciousness status (ACVPU), limitation on activities due to COVID-19, and requirements for 
Ongoing hospital medical careSupplemental oxygennon-invasive ventilation or a high flow oxygen devicemechanical ventilationextracorporeal membrane oxygenation, oradditional organ support (e.g. pressors, renal replacement)
Clinical symptoms and interventions of interest		Daily										X	X			See Table 1 for clinical symptoms and interventions of interest.

Procedures	Screening	Evaluation Period										ETV	Post-Evaluation Follow-Up			Comments
Study Day	Max 7-day window	1	2-7	8	15	22	29	36	43	50	57		85	141	169	
Visit window (\pm number of days)	--	--	--	2	2	2	2	2	2	2	2		7	7	7	
Symptoms Questionnaire	X	Daily										X	X		See Section 8.1.2.	
SARS-CoV-2 POC Test (Nasal Swab)	X														Applies to participants in Part 2 only. Result must be determined prior to collecting swabs for PCR test.	
SARS-CoV-2 Serology		X				X			X	X	X	X	X	X	Day 1: pre-dose. assessed at a central laboratory	
SARS-CoV-2 nasopharyngeal swab (for PCR test) taken from both nostrils		X													Day 1: pre-dose. assessed at a central laboratory	
SARS-CoV-2 nasal swab (for PCR test) taken from both nostrils		X		X	X	X	X	X	X	X	X	X	X		Day 1: pre-dose. assessed at a central laboratory No samples needed if participant is hospitalized.*	

Procedures	Screening	Evaluation Period										ETV	Post-Evaluation Follow-Up			Comments
Study Day	Max 7-day window	1	2-7	8	15	22	29	36	43	50	57		85	141	169	
Visit window (\pm number of days)	--	--	--	2	2	2	2	2	2	2	2		7	7	7	

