### **6.1.3. Study Time Intervals**

To calculate the length of any time interval or time period in this study, the following formula will be used:

$$\text{Length of interval (days)} = \text{End Date} - \text{Interval Start Date} + 1$$

To convert any time length from days to weeks, the following formula will be used:

$$\text{Length of interval (weeks)} = \text{Length of interval (days)}/7$$

Only for the purpose of calculating the length of study period time intervals, the words “prior to” in [Table PYAD.6.2](#) should be understood to mean “the day before” while the words “after” should be understood to mean “the day after.” For the purpose of determining whether a date/time lies within an interval, these words are intended to convey whether the start or end of the period is inclusive of the specified date.

For the purposes of the endpoints assessing the incidence of SARS-CoV-2 infection, the words “by Day 29” should be understood to mean “at any time prior to and including the Day 29 visit, provided the visit occurs within the specified visit window.” The words “by Day 57” should be understood to have a similar meaning. For all other endpoints, similar definitions will apply, but results from visits outside of the specified visit window may be used.

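### The missing-swab rule in SAP 6.3.1, read literally, scores a participant with a recorded positive RT-PCR and a later missing swab as a non-event, against the SAP's own endpoint definitions

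*SAP*

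**What the plan says.** SAP 6.3.1 first excludes Prevention-population participants with no post-baseline RT-PCR result. Its next rule covers a participant with at least one result who "has not yet tested positive or is missing additional test results during the time frame of the endpoint". That participant is set to negative at the visits before the last available test and "will be treated as not experiencing the event of interest in the primary and key secondary analyses". The section is headed "Missing SARS-CoV-2 Infection Status".

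SAP 6.3.2 has a parallel rule for disease status. It covers a participant who has not yet met the COVID-19 criteria, or who "is missing data used to determine COVID-19 status, the participant will be treated as not experiencing COVID-19". The same logic is extended to moderate-or-worse disease.

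The endpoint definitions are elsewhere in the SAP:

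- **6.1.3:** for infection, by Day 29 means "at any time prior to and including the Day 29 visit, provided the visit occurs within the specified visit window"; Day 57 is read in the same way.
- **6.10.3.2:** the key secondary infection endpoint is "the proportion of patients in the Prevention populations who are SARS-CoV-2 positive postbaseline" by Day 29.
- **6.10.1:** "The endpoint for the primary analysis is defined as the first occurrence of COVID-19" by Day 57.

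The Schedule of Activities (Protocol 1.3.1) plans weekly nasal swabs from Day 8 to Day 57, with the comment "No samples needed if participant is hospitalized".

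**The concern.** Because the conditions are joined by *or*, the second is enough on its own. A participant with a laboratory positive inside the window who lacks any further in-window result falls under the rule and becomes a non-event. Later swabs play no part in the infection endpoint, so their absence should not cancel a positive.

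Later results can be absent for several reasons: a missed visit, death, a hospital stay, or the event-triggered Primary Database Lock (SAP 6.1.5), which is taken while some participants are still in the Evaluation Period. Hospital stay and death are tied to severity, so the loss need not be random.

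Infection by Day 29 is in the multiplicity-controlled family (SAP 6.5). A programmer who followed 6.3.1 to the letter would remove observed infections from a confirmatory test.

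**Working it through.** **1. The rule against the endpoint.** The four possible cases for infection by Day 29 are:

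| In-window positive on record | Later in-window result missing | Literal 6.3.1 | 6.1.3 with 6.10.3.2 |
|---|---|---|---|
| No | No | Non-event | Non-event |
| No | Yes | Non-event | No positive on record, so not counted |
| Yes | No | Rule does not apply; event | Event |
| Yes | Yes | **Non-event** | **Event** |

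Only the last row conflicts. If the rule is limited to participants with no positive result, that row becomes an event and the other three do not change.

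The instruction to set earlier visits to negative adds to the difficulty. Take a participant positive on Day 8, missed on Day 22 and swabbed on Day 29. Read literally, it overwrites the Day 8 result.

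**2. Which endpoints are exposed.** For infection by Day 29, 6.3.1 is the governing rule and the conflict is direct. 6.3.1 also names the primary endpoint, but 6.3.2 is the more specific rule for COVID-19 and moderate-or-worse disease. Its second condition is limited to data needed to determine status. Once detection and qualifying severity within 21 days are recorded, a later swab is not such data. The exposure there is weaker, but 6.3.2 has the same *or* and also makes no exception for criteria already met.

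**3. The plan's own event figure.** The Part 1 inputs in SAP 5.2 are two-sided 0.05, 90% power and risk ratio 0.33; Protocol 6.3 gives 1:1 allocation. Schoenfeld's formula gives 4 × (1.960 + 1.282)² / (ln 0.33)² = 34.2 events. The stated 33 events give 89% power. The plan's figure is reproduced closely and does not depend on the wording at issue.

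**4. Illustrative size for infection by Day 29.** The documents give no missed-swab rate, so q is an assumption. Four post-baseline swabs are planned by Day 29 (Days 8, 15, 22 and 29). Assume that first positives are spread evenly over them and that each later swab is missed independently with probability q. A first positive on Day 8, 15, 22 or 29 leaves k = 3, 2, 1 or 0 later swabs. The fraction reversed is the mean of 1 − (1 − q)^k:

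- q = 2%: (0.0588 + 0.0396 + 0.0200 + 0) / 4 = 0.030
- q = 5%: (0.1426 + 0.0975 + 0.0500 + 0) / 4 = 0.073
- q = 10%: (0.2710 + 0.1900 + 0.1000 + 0) / 4 = 0.140

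**5. Direction of bias.** If fractions L_A (active) and L_P (placebo) of the events are reversed, the observed ratio is 0.33 × (1 − L_A) / (1 − L_P). Equal loss leaves 0.33 unchanged. Purely to show direction, 30% loss on placebo and 10% on active gives 0.33 × 0.9 / 0.7 = 0.42. The opposite pattern gives 0.33 × 0.7 / 0.9 = 0.26. The effect could be diluted or overstated.

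**The case against.** The strongest reply is that the sentence was never meant for participants with a positive. The heading concerns missing infection status, and someone with an in-window positive has none missing. *Not yet* and *additional* describe a person negative so far. Filling in earlier negatives makes sense only for such a person. The supplementary analysis in the same section ties missing status to death, discontinuation or the lock. The endpoint definitions, and the Cox analysis of first incidence in 6.10.2.2, all count a recorded event. This is persuasive on intent, and it stands. It does not remove the fault: 6.3.1 is the operative instruction for these analyses, it has no exception, and the SAP does not say which section prevails.

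A reader might infer four stronger things, which the documents do not support:

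- **That the SAP has settled on scoring such positives as non-events.** It has not; the sections conflict.
- **That the 33 events would shrink to about 28.** This takes the Day 57 version of step 4 (8 swabs, q = 5%, about 16% reversed) and applies it to 33. In 6.1.5.1, 33 is a count of moderate-or-worse cases, for which 6.3.2 is the specific rule. The lock is also event-driven: if the trigger used the same scoring, accrual would continue to 33 counted events unless the slow-accrual fallback applied. A loss of power is not established.
- **That every hospitalized positive would certainly be reversed.** The schedule requires no sample in hospital, and the SAP does not say whether a swab that was not required counts as missing.
- **That the primary endpoint is as exposed as infection.** Step 2 shows that it is not.

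**Conclusion.** The point holds as a conflict between a stated missing-data rule and the SAP's own endpoint definitions. Applied literally, 6.3.1 turns an in-window positive with a later missing swab into a non-event. The context indicates that this was not intended.

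The size is unknown. The 3%, 7% and 14% for missed-swab rates of 2%, 5% and 10% rest on evenly spread first positives, independent misses and literal programming. They leave out hospital stays, deaths and the lock as separate causes. No event target, sample size, significance level or endpoint definition is wrong because of this wording. It should still be corrected, because the rule governs a multiplicity-controlled endpoint and gives a wrong result if coded as written.

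**What to change.** Reword SAP 6.3.1 so that the negative and non-event imputation applies only to a participant with at least one post-baseline RT-PCR result and no positive among the available results in the endpoint window. Add that any post-baseline positive in the window is an infection event, whatever later results are missing.

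Reword SAP 6.3.2 in the same way: a participant whose recorded data already meet the COVID-19 or moderate-or-worse criteria is an event, whatever other data are missing.

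The cost is about one sentence in each section, plus a check that the analysis programs agree. Data collection, design, event targets and sample size do not change.
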